## **2. Introduction**

### **2.1. Background and rationale**

Up to 95% of people in AOD treatment smoke tobacco. People with substance use disorders experience great difficulty quitting tobacco smoking. As a result, quit rates are close to zero, and tobacco-related diseases are the leading cause of mortality. New ways for addressing smoking in this population are needed. Vaporised nicotine products (VNPs) hold significant potential as both cessation aids and harm reduction support. There is now good evidence of safety, and emerging evidence that VNPs assist cessation. More evidence of the safety and effectiveness of VNPs for populations with high smoking prevalence rates and low quit rates is desperately needed. Many AOD withdrawal facilities are smoke-free, and service users achieve brief abstinence. However, most return to smoking immediately following discharge, representing a missed opportunity for supporting long-term abstinence. Providing smoking cessation support post discharge will assist individuals with moderate to heavy nicotine dependence to remain smoke-free in the community. The aim of this world-first trial is to test the effectiveness of VNPs at increasing smoking cessation amongst AOD residential withdrawal services. Service users (n=926) from six residential and inpatient withdrawal AOD services across three states (NSW, Victoria, and Queensland) will be recruited and randomised. Participants in the comparison condition will receive current best-practice combination nicotine replacement therapy (NRT). Participants in both groups will also receive proactive Quitline support from AOD-trained counsellors. The trial will build on our pilot study in a Victorian AOD withdrawal facility which found the design and the interventions highly feasible and acceptable to both service users and staff.

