#### **2.2.2. Secondary objectives**

Additional secondary objectives are to compare participants in the VNP + Quitline to those in the NRT + Quitline group on:

- i) Biochemically verified 7-month continuous abstinence at month 9
- ii) 30-day point prevalence abstinence at months 3 and 9
- iii) Reduction in cigarettes smoked per day at months 3 and 9
- iv) Reduction in strength and urges to smoke tobacco at months 3 and 9
- v) Reduction in withdrawal symptoms at months 3 and 9
- vi) Relapse episodes to smoking at months 3 and 9

Other objectives involve:

- i) Assessing treatment adherence (duration/ use of products/ reasons for non-use/ engagement with telephone counselling) compared by treatment group
- ii) Assess attitudes/ acceptability of the provided interventions
- iii) Use of additional pharmacotherapies, visits to GPs, and use of print and online materials
- iv) Assess provided interventions on mood

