Nicotine withdrawal symptoms over past 24hours was measured at baseline and 3-month follow-up using the Minnesota Nicotine Withdrawal Scale (MNWS), with symptoms [angry, irritable frustrated; anxious or nervous; depressed or sad; desire or craving to smoke; difficulty concentrating; increased appetite, hungry or weight gain; insomnia, sleep problems or awakening at night; restless or impatient] experienced in last 24 hours rated on an ordinal scale ranging from 0 (none), 1 (mild), 2 (moderate), to 3 (severe).

- Last 30 days (past week assessed at baseline; last 30 days at 3-month and 9-month follow-up)

A modified version of the MNWS was used to assess withdrawal symptoms over past 30 days. At baseline participants were asked "In the week before you came here, how often were you bothered by the following problems", and at 3-month and 9-month

follow-up timepoints “In the last 30 days, how often were you bothered by the following problems?” and asked to rate the list of withdrawal symptoms from 0 (not at all), 1 (several days), 2 (more than half the days), to 3 (nearly every day).

vii) Relapse episodes

- **Instance of relapse at 3-month follow-up** will be determined by:  
Answering ‘daily’ or ‘yes, at least once a week’ to question of “*do you currently smoke any tobacco products*”  
OR  
Answering ‘less often than once a week’ or ‘not at all’ to current smoking status **AND** answering ‘yes’ to question “*since you left service, have you smoked every day for a week or more?*”
- **Time to relapse at 3-month follow-up** is assessed by the question “How soon after discharge did you go back to smoking (your first smoke after discharge)?” with response options a) as soon as I could get a cigarette that day; b) later on the day I got out; c) on the day after I got out; d) 2-7 days after I got out; e) more than a week after I got out but less than 1 month; f) more than a month after I got out.
- **Instance of relapse at 9-month follow-up** is determined by:  
Answering ‘not at all’ to *current smoking status* **AND** responding ‘yes’ to question “*Since you quit smoking, have you smoked every day for a week or more (even just puffs)? (yes/no)*”  
OR  
Current (daily or occasional) smokers who report a quit attempt within past 6 months that lasted  $\geq 2$  days

vii) Abstinence from all nicotine/ tobacco products

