#### 4.3.2. Secondary outcome models

Secondary abstinence outcomes will be assessed in the ITT population, other secondary outcomes in the completers and the ITT population. GLMM will be used to assess the difference in outcomes at follow up between treatment groups or changes from baseline.

All single endpoint outcomes will include a normally distributed random intercept for site (on the scale of the canonical link function for the specific distribution family) and treatment group as a fixed effect with a non informative prior for the treatment effect. The random intercept will be modelled from a normal distribution with mean 0 and a hierarchical variance parameter that is distributed as a half Student-T of 3 degrees of freedom.

For outcomes with multiple time points, the models will additionally include participant id as a random intercept, and parameters for time with an interaction between time and treatment group as fixed effects, all on the scale of the canonical link function for the specific distribution family. Non-informative priors will be used for fixed effects. Participant id

random intercept will be modelled from a multivariate normal distribution with mean 0 and covariance matrix with a non-informative prior (LKJ-Correlation and half Cauchy priors implemented in the brms R package).

A GLMM with a binomial distribution and logit link function will be used to model abstinence outcomes (biochemically verified 7-month continuous abstinence, self-reported 30 day and 7 day point prevalence, abstinence at 3 and 9 months).

Number of cigarettes smoked per day will be compared at each time point using a GLMM with a negative-binomial distribution and log link function. Percentage reduction of at least 50% in the number of cigarettes smoked per day will be assessed with GLMM with a binomial distribution and logit link function.

Craving scores and relapse episodes will be compared using a GLMM with multinomial distribution and a cumulative logit link function, or binomial distribution and logit link depending on the distribution of responses.

Withdrawal scores will be compared using a GLMM with normal distribution and identity link function.

Abstinence from all nicotine/ tobacco products will be modelled using GLMM with a binomial distribution and logit link function.

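### The 9-month relapse rule counts a current smoker only if there was a recent quit attempt, so continuous smokers are grouped with abstainers and the arm difference is diluted and can reverse

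*SAP*

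**What the plan says.** SAP section 2.2.2 lists one relapse objective covering both surveys: "Relapse episodes to smoking at months 3 and 9". Section 4.1.2, item vii, defines relapse separately for each survey.

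- **Month 3.** The first route is "Answering ‘daily’ or ‘yes, at least once a week’ to question of" current smoking, with no further condition. The second covers less-than-weekly smokers and non-smokers who report at least a week of daily smoking since leaving the service.
- **Month 9.** The first route covers people not smoking at all who answer yes to "Since you quit smoking, have you smoked every day for a week or more (even just puffs". The second is "Current (daily or occasional) smokers who report a quit attempt within past 6 months that lasted" at least 2 days. There is no third route.
- **Time to relapse (month 3).** The item asks "How soon after discharge did you go back to smoking (your first smoke after discharge". Its six answers run from the day of discharge to more than a month later; none is for a person who has not smoked.

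Section 4.3.2 analyses "other secondary outcomes in the completers and the ITT population", which includes relapse. For the model it says "Craving scores and relapse episodes will be compared using a GLMM with multinomial distribution and a cumulative logit link function", or a binomial model with logit link, depending on the responses. It names no at-risk subset, no carry-forward of month-3 relapse and no separate category for smokers without a recent attempt.

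**The concern.** A person who resumed smoking on the day of discharge and smoked daily for nine months is relapsed at month 3. At month 9 that person meets neither route and, with no other category or exclusion given, sits with the sustained abstainer. A smoker who managed a few days off cigarettes in the past six months is counted as relapsed. Among smokers, then, the month-9 outcome measures recent quit attempts, not smoking.

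The people misplaced may be most of the sample. Section 2.1 says "Many AOD withdrawal facilities are smoke-free, and service users achieve brief abstinence", and adds that most go straight back to smoking on leaving. Section 3.4 plans for only 3% and 9% continuous abstinence.

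At stake is the direction of a listed secondary comparison. An arm with fewer smokers could show more relapse if its remaining smokers try to quit more often. The month-3 and month-9 results also cannot be read as one outcome over time.

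**Working it through.** **1. The two rules side by side**

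| Status at the survey | Month 3 | Month 9 |
|---|---|---|
| Daily or weekly smoker, no quit attempt of at least 2 days in the past 6 months | Relapsed | Meets neither route |
| Daily or weekly smoker with such an attempt | Relapsed | Relapsed |
| Less-than-weekly smoker | Relapsed if a week or more of daily smoking since leaving | Relapsed only with such an attempt |
| Not smoking, but a week or more of daily smoking (since leaving at month 3, since quitting at month 9) | Relapsed | Relapsed |
| Not smoking, no such week | Not relapsed | Not relapsed |

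At month 9 the first and last rows fall together.

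**2. Inputs**

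The SAP gives no expected figure for relapse. Its sample size (section 3.4) does not depend on relapse and reproduces: 278 per arm with a continuity correction, and 556/0.60 = 926.7 against 926 stated. The illustration uses:

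- a, the share not smoking at month 9: 3% NRT and 9% VNP. These are the section 3.4 rates for *continuous abstinence*, used as stand-ins; current non-smoking could be higher.
- r, the share of non-smokers with a week or more of daily smoking since quitting: 20%, assumed.
- q, the share of current smokers with a qualifying attempt: varied, assumed.
- s, the share of current smokers counted under a month-3-type rule: 100%, or 80% if some smoke less than weekly and do not qualify.

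**3. Formulas**

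Relapse under the written rule = a·r + (1 − a)·q. Relapse under a current-smoking rule = a·r + (1 − a)·s.

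**4. Unequal attempt rates (q = 30% NRT, 40% VNP)**

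- Written rule, NRT: 0.03 × 0.20 + 0.97 × 0.30 = 29.7%.
- Written rule, VNP: 0.09 × 0.20 + 0.91 × 0.40 = 38.2%. Difference +8.5 points; VNP looks worse.
- All smokers counted: 0.006 + 0.97 = 97.6% vs 0.018 + 0.91 = 92.8%. Difference −4.8 points; VNP looks better.
- With s = 80%: 78.2% vs 74.6%, difference −3.6 points.

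**5. Equal attempt rates**

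The difference, VNP minus NRT, reduces to (0.09 − 0.03)·(r − q).

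| q in both arms | r = 20% |
|---|---|
| 50% | −1.8 points |
| 30% | −0.6 points |
| 20% | 0.0 points |
| 0% | +1.2 points (0.6% vs 1.8%) |

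All but the last are dilutions of −4.8, the q = 20% case to nothing; the sign changes only when r exceeds q. With r = 30% and q = 20% the difference is +0.6.

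**6. How little is needed to reverse**

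With r = 20% and NRT q = 30%, the sign changes once VNP q exceeds (0.297 − 0.018)/0.91 = 30.7%. With NRT q = 50%, it changes above (0.491 − 0.018)/0.91 = 52.0%.

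**7. Other non-smoking rates**

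With a = 10% and 20%, r = 20%, and q = 30% and 40%, the written rule gives 29.0% vs 36.0% (+7.0). Counting all smokers gives 92.0% vs 84.0% (−8.0).

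**The case against.** The best defence is that month 9 is meant to record new episodes. The item is headed as relapse episodes, the six-month look-back equals the gap between the two surveys, and continuous smokers were already counted at month 3. That is a coherent construct, but the SAP neither states it nor restricts the denominator to people who could have a new episode. It would also leave a hole: someone abstinent from discharge to month 5 who then smoked on began that quit more than six months before the survey, and may be missed at both visits.

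Other points on that side stand and limit the claim:

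- A reader might infer that reversal is bound to happen. It is not; with equal attempt rates above r the effect is only diluted.
- A reader might infer that the SAP puts both definitions into one time-by-treatment model. That follows only from the general sentence on outcomes with multiple time points in section 4.3.2. The relapse sentence mentions no time term.
- A reader might infer that the full month-3 rule can simply be applied at month 9. The SAP lists the item on daily smoking since leaving the service only for month 3. A rule counted from discharge would also mark as relapsed some people whom the primary outcome, with its roughly two-month grace period, counts as abstinent.
- A reader might infer that time to relapse will compare only those who smoked. The SAP describes neither the routing nor a specific model for that item, and no listed item clearly identifies people who have not smoked since discharge.

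**Conclusion.** The month-9 rule is faulty as written; this is more than a missing detail. It follows from the two routes and the absence of a risk set that continuous smokers share a class with abstainers, although the SAP does not print that label for them.

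The certain consequence is that relapse means different things at months 3 and 9. The likely consequence is a between-arm difference pulled towards zero. The possible consequence is a change of sign, for which a gap in attempt rates of under one point can suffice when the NRT rate is 30%. Those sizes rest on assumed attempt rates, an assumed r, and planning abstinence rates standing in for current non-smoking. They show what the rule can do and do not predict the trial's result.

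The abstinence outcomes still show independently which arm smokes less.

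**What to change.** Before the relapse analysis is run, amend section 4.1.2, item vii, and the matching text in section 4.3.2:

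1. At month 9, score every current daily or weekly smoker as relapsed, as at month 3. The current-smoking item in section 4.1.1 already supplies this.
2. For non-smokers, keep the existing month-9 item anchored on when the person quit; it is compatible with the primary outcome's grace period.
3. For less-than-weekly smokers, state a rule using an item that was collected, for example the month-3 answer or time since last daily smoking.
4. Report quit attempts of at least 2 days followed by smoking as a separate outcome with its own denominator.
5. Do not model month-3 and month-9 relapse together with a time-by-treatment term unless the definitions match.
6. For time to first smoke, place respondents identifiable as not having smoked since discharge in the highest category, if the collected data allow it. Otherwise state who is excluded.

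The main change costs only SAP wording and derivation code. Items 3 and 6 depend on what the questionnaires hold, which the SAP does not fully show.

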#### 4.1.2. Secondary outcomes

i) Biochemically verified 7-month continuous abstinence from tobacco smoking (dichotomous: abstinent or not)

- Self-reported 7-month continuous abstinence at 9-month survey will be verified using measures of CO in expired air. A cut-off point of 8ppm will be used to define a smoker (i.e. CO level <8ppm will be considered biochemically verified abstinent).

ii) 30-day point prevalence abstinence (PPA)

- Two items will be used to assess self-reported 30-day PPA: "Have you smoked at all, even a puff, in the last 30 days?" (response options: yes; **no**), and "How many cigarettes have you smoked in the last 30 days?" (response options: **less than 1 or just a puff**; 1 – 5; 6 – 10; 11 – 20; more than 20).

Participants who report not having smoked in the last 30 days AND smoking 'less than 1' cigarette or 'just a puff' in last 30-days will meet 30-day PPA criteria.

iii) 7-day PPA

- Self-reported 7-day PPA will be measured by asking participants "Have you smoked at all, even a puff, in the last 7 days?" with response options a) yes, b) no. Responding 'no' will equate to self-reported 7-day PPA.

iv) Number of cigarettes smoked and percentage reduction from baseline (dichotomised: at least 50% or < 50%)

- Participants will be asked "currently how many cigarettes do you smoke per day, per week, and per month?".
- Only asked of participants who report that they are occasional/ daily smoking (if the participant reports quitting in the primary outcome they are excluded from this analysis)
- Percentage reduction in number of cigarettes smoked from baseline (dichotomised: at least 50% or < 50%)
- Reduction rate also to be calculated

v) Reducing cravings to smoke

- Frequency of cravings was assessed by one item^3: "How often do you get cravings to smoke tobacco?" with response options: a) hourly or more often, b) several times per day, c) at least once a day, d) less than daily, or e) never.

vi) Reducing withdrawal symptoms (24 hours, 30 days)

- 24 hours (measured at baseline and 3 months)

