- This will be measured by asking participants "Are you currently using any form of nicotine products, including vapourised nicotine products and tobacco products other than cigarettes? Check all that apply" with response options a) no; b) yes, nicotine patches; c) yes, oral nicotine products; d) yes, nicotine vaping products; e) yes, some other form of tobacco product. Responding ‘no’ will equate to ‘Abstinence from all nicotine/ tobacco products.’

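### Abstinence from all nicotine and tobacco is scored from an item that leaves out cigarettes, so as written a smoker who uses nothing else counts as abstinent

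*SAP*

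**What the plan says.** SAP section 4.1.2 lists the outcome as "vii) Abstinence from all nicotine/ tobacco products". It is measured by one question on current use of nicotine products, with the scope "including vapourised nicotine products and tobacco products other than cigarettes". Respondents tick all that apply from: "a) no; b) yes, nicotine patches; c) yes, oral nicotine products; d) yes, nicotine vaping products; e) yes, some other form of tobacco product". The scoring rule is: "Responding ‘no’ will equate to ‘Abstinence from all nicotine/ tobacco products".

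Section 4.3.2 gives the outcome its own model: "Abstinence from all nicotine/ tobacco products will be modelled using GLMM with a binomial distribution and logit link function". The same section sets the analysis population: "Secondary abstinence outcomes will be assessed in the ITT population, other secondary outcomes in the completers and the ITT population". Under section 4.5, participants with missing data are taken as not abstinent in the main analysis.

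**The concern.** The label covers all nicotine and tobacco, but the question sets cigarettes aside and the scoring rule does not bring them back. A programmer who follows the text would code as a success someone who smokes cigarettes every day and uses nothing else.

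In a trial of vaping products this outcome matters more than its place in the list suggests. It is the only listed outcome that shows whether participants end up free of nicotine altogether or move from smoking to another product. Under the written rule it mixes two opposite groups: people who use nothing, and smokers who have dropped their cessation aid or never used it.

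**Working it through.** The plan gives no figure for this outcome, so there is none to reproduce. The finding comes from tracing the rule; the arithmetic only shows how large the error could be.

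**Tracing the rule**

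1. Take a participant who smokes cigarettes daily and uses no patch, oral nicotine, vaping product or other tobacco.
2. The question excludes cigarettes, and none of the four yes options describes this person. The accurate answer is no.
3. No is scored as abstinent, with no second condition.
4. The participant is in the intention-to-treat population and enters the binomial model as a success.

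**Comparing with neighbouring definitions in section 4.1.2**

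- The primary outcome combines current smoking status with time since last daily smoking, and both must be met.
- 30-day point prevalence and the relapse definitions also use explicit combined conditions.
- The cigarettes-per-day item states its filter: "Only asked of participants who report that they are occasional/ daily smoking".
- The all-nicotine outcome has neither a combined condition nor a filter.

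**Illustration of size**

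Inputs:

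- Follow-up of 60%, from the 40% attrition in section 3.4. The plan's own use of that figure reproduces: 2 × 278 / 0.60 = 926.7, against the stated 926.
- Non-respondents scored not abstinent (section 4.5), so they add no false successes.
- Assumption: 20% of respondents currently do not smoke. The plan gives no rate for this.
- Assumption: a share *s* of the remaining smokers use cigarettes only, varied from 20% to 80%.

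Smokers with a response, as a share of those randomised: 0.60 × (1 − 0.20) = 0.48. Falsely scored abstinent: 0.48 × *s*. If every non-smoking respondent is also nicotine-free, the correctly scored share is 0.60 × 0.20 = 0.12.

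| *s* | Falsely abstinent, of randomised | Scored abstinent | False share of those scored abstinent |
|---|---|---|---|
| 20% | 9.6% | 21.6% | 44% |
| 50% | 24.0% | 36.0% | 67% |
| 80% | 38.4% | 50.4% | 76% |

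If some non-smokers still use nicotine, the last column rises. Among respondents alone, the falsely scored share is 0.80 × *s*, or 16% to 64%.

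**Difference between arms**

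With the same follow-up and smoking rates in both arms, the spurious difference (NRT minus VNP) is 0.48 × (*s* in NRT − *s* in VNP). Equal shares give 0. Shares of 70% (NRT) and 40% (VNP) give 33.6% − 19.2% = 14.4 points. Swapping them gives 14.4 points the other way. The documents do not say which case applies.

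**The case against.** The best defence is a survey filter that the SAP does not state. The phrases about products other than cigarettes and other forms of tobacco read like a follow-on to the smoking-status question. The SAP does leave some routing unstated: the time-to-relapse item in section 4.1.2 has no option for someone who never went back to smoking. If only non-smokers were asked, smokers would have no response, and section 4.5 would score them not abstinent in the main analysis.

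This is possible, and it means one cannot say that smokers certainly will be counted. It does not rescue the written rule, which mentions no filter. Even with a filter, smokers would be right only by being treated as missing: an analysis imputing under missing at random, as section 4.4 plans for secondary outcomes, could assign them values as though their status were unknown.

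It can also be said that a smoker may regard cigarettes as a nicotine product and tick something. The wording excludes that reading and no option fits it, so inconsistent answers would only add noise.

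The point about weight stands. The outcome is secondary, it is absent from the objectives in section 2.2.2, and the data needed to score it correctly are already collected.

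**Conclusion.** The definition is wrong as written. A current cigarette smoker who uses no other product is scored abstinent from all nicotine and tobacco, and the modelled result would not measure what it is called. This rests on the text alone. The size does not: about 10% to 38% of those randomised falsely scored abstinent holds only under the assumed 20% non-smoking among respondents, the 20% to 80% range for cigarette-only use, and the planned 40% attrition.

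Two stronger readings are tempting, and the documents do not support them.

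- A reader might infer from section 3.4 that more than 90% will still be smoking, and that true nicotine-free abstinence cannot exceed 9% (VNP) or 3% (NRT). Those are planning rates for continuous abstinence. Someone who relapsed and quit again fails that measure but is not smoking now, so current non-smoking can be higher, and the plan gives no rate for it. Figures built on 91% and 97% still smoking also overstate the error if they ignore attrition. With assumed cigarette-only shares of 40% and 70%, 0.91 × 0.40 = 36% and 0.97 × 0.70 = 68% become about 22% and 41% after multiplying by 0.60.
- A reader might infer that the error favours a particular arm or would reverse the comparison. That depends on how many smokers in each arm use cigarettes only, which is unknown.

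The primary outcome is unaffected. This should be fixed before analysis but does not threaten the trial's main conclusion.

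**What to change.** In section 4.1.2, define the outcome by two conditions at the same time point: the not-at-all response to the current tobacco smoking item, and no to the nicotine-product item. State that current smokers are scored as not abstinent even if a survey filter means they are not asked the second item. Missing responses otherwise follow section 4.5. If a filter exists, the SAP should describe it.

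The cost is a sentence or two in the SAP and a matching line in the derivation code. Both items are already collected, and the model in section 4.3.2 does not change.
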